8.3.2 Efficacy Assessments

Subjects will report efficacy assessments via an interactive voice response system (IVRS) utilizing a touch-tone telephone. Efficacy assessments will be collected daily and weekly, unless otherwise specified, from the beginning of the screening period through the end of the treatment period. The daily questions will include information about bowel movement frequency, completeness of bowel emptying, stool consistency, straining, abdominal pain, abdominal discomfort, abdominal bloating, abdominal fullness, abdominal cramping, and use of rescue medications. IBS severity and constipation severity will be collected weekly during the screening and treatment periods. Adequate relief of IBS symptoms and degree of relief of IBS symptoms will be collected weekly during the treatment a period. Treatment satisfaction (Visits 4, 5, 6, 7, 8, and 9) and IBS-QOL (Visits 2, 6, and 9) will also be evaluated during the subjects' site visit.

A script detailing the IVRS diary questions and scales will be supplied to the clinical site and to the subjects in the form of written subject information material. The following questions will be asked to all subjects on a daily or weekly basis during the screening and treatment periods.

8.3.2.1 Abdominal Pain

“How would you rate your worst abdominal pain over the past 24 hours? Please use the scale where 0 represents no abdominal pain and 10 represents very severe abdominal pain. Please enter a value between 0 and 10 followed by pound or hash sign.”

8.3.2.2 Abdominal Discomfort

“How would you rate your abdominal discomfort over the past 24 hours? Please use the scale where 0 represents no abdominal discomfort and 10 represents very severe abdominal discomfort. Please enter value between 0 and 10 followed by pound or hash sign.”

8.3.2.3 Abdominal Bloating

“How would you rate your abdominal bloating over the past 24 hours? Please use the scale where 0 represents no abdominal bloating and 10 represents very severe abdominal bloating. Please enter a value between 0 and 10 followed by pound or hash sign.”

8.3.2.4 Abdominal Cramping

“How would you rate your abdominal cramping over the past 24 hours? Please use the scale where 0 represents no abdominal cramping and 10 represents very severe abdominal cramping. Please enter a value between 0 and 10 followed by pound or hash sign.”

8.3.2.5 Abdominal Fullness

“How would you rate your abdominal fullness over the past 24 hours? Please use the scale where 0 represents no abdominal fullness and 10 represents very severe abdominal fullness. Please enter a value between 0 and 10 followed by pound or hash sign.”

8.3.2.6 Bowel Movement Frequency

“How many bowel movements have you had in the past 24 hours?”

8.3.2.6.1 Timing

“Please enter the time of bowel movement <number> using the 12 hour AM/PM format.”

“For AM press 1, for PM press 2.”

8.3.2.6.2 Sensation of Complete Bowel Emptying (For each bowel movement)

“Did you feel like you completely emptied your bowels? For yes press 1 for no press 2.”

8.3.2.6.3 Stool Consistency using BSFS ([Appendix B](#)) (For each bowel movement)

“Refer to the Bristol Stool Form Scale given to you. Please enter the number that best describes the consistency of bowel movement <number> following the scale:

Press 1 for separate hard lumps, like nuts (hard to pass)

Press 2 for sausage shaped but lumpy

Press 3 for like a sausage but with cracks on its surface

Press 4 for like a sausage or a snake, smooth and soft

Press 5 for soft blobs with clear cut edges (passed easily)

Press 6 for fluffy pieces with ragged edges, a mushy stool

Press 7 for watery, no solid pieces (entirely liquid)”

8.3.2.6.4 Straining (For each bowel movement)

“How much did you strain during the bowel movement? Please use the following scale. Press 1 for not at all. Press 2 for a little bit. Press 3 for a moderate amount. Press 4 for a great deal. Press 5 for an extreme amount.”

8.3.2.7 Rescue medication

If diary was completed the previous day “Have you taken any rescue medication over the past 24 hours? For yes press 1, for no press 2.”

If diary was NOT completed the previous day “Have you taken any rescue medication over the past 48 hours? For yes press 1, for no press 2.”

If yes. “Please enter the date you took the rescue medication, using the 8 digit format; 2 digits for the month, 2 digits for the day and 4 digits for the year.”

“Please enter the time you took rescue medication, using a 12 hour AM/PM format.”

“For AM press 1, for PM press 2”

The following questions will be asked once at the end of each week; when these questions are asked they will be the first questions asked to the subjects

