4. INVESTIGATIONAL PLAN

This is a Phase 3, multi-center, randomized, double-blind, placebo controlled study of tenapanor in subjects with IBS-C. Patients who are 18 to 75 years old, meeting the definition of IBS-C as defined by the Rome III Criteria for the Diagnosis of IBS (see [Appendix A](#)) will undergo a battery of screening procedures to determine eligibility for the trial. A 2:1 screen to randomization ratio is expected.

The study will consist of a 2-week screening period, and a 26-week treatment period.

Two weeks prior to study randomization, prospective subjects may be assessed with respect to their meeting the eligibility requirements of the study.

At the beginning of the 2-week screening period (Day -14), subjects will be questioned with respect to their eligibility for the study. Those that meet the basic requirements will be asked to provide written informed consent. The basic screening assessments will include: evaluation of the inclusion/exclusion criteria, medical history (including details about co-morbid disorders), physical exam, vital signs, ECG, and clinical laboratory tests, including urinalysis. Subjects must discontinue the use of all prohibited medications at Visit 1 (Screening/Day -14) for the duration of the study, as referenced in [Section 5.6](#). During the screening period, and starting on the evening of Study Visit 1, subjects will self-report daily information about the status of their IBS symptoms via a touch-tone telephone diary. Each day, entries into the telephone diary (IVRS diary) must occur between 6PM and 11:59PM (local time). This will include information about their stool frequency, stool consistency, straining, abdominal pain, abdominal discomfort, abdominal bloating, abdominal fullness, abdominal cramping, and rescue medication usage. Additionally, on a weekly basis, the IBS severity and constipation severity will also be collected through the IVRS diary. Subject compliance with the electronic diary will be monitored actively by the site staff and by the electronic diary system.

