5.5. Rescue Medication

The following rescue medications are allowed for severe constipation (ie, at least 72 hours after the subject's previous BM or when symptoms become intolerable):

- Bisacodyl (5 mg tablet or 10 mg suppository)

Rescue medication is allowed during the screening period, provided that there are no more than 2 uses and that none is used during the 2 days before randomization.

Subjects are instructed to contact the investigator prior to taking a rescue medication for severe constipation, and all rescue medication usage and time of usage must be recorded during the subject's daily call to the IVRS. A bowel movement will not be considered a spontaneous bowel movement (SBM) if it is reported less than 24 hours from the use of a rescue medication.

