8.1.2 Daily Patient Reported Outcomes (PRO) (Day –14 through Day 183)

Subjects must assess their IBS symptoms daily via the touch-tone telephone diary system between 6PM and 11:59PM (local time):

- Frequency and time of each Bowel Movement (BM)

The following characteristics of each BM

- Sensation of complete bowel emptying
 - Stool consistency (BSFS) of each BM
 - Severity of straining for each BM
- Abdominal pain
 - Abdominal discomfort
 - Abdominal bloating
 - Abdominal fullness
 - Abdominal cramping
 - Use of and time of rescue medication
 - IBS severity (weekly)
 - Constipation severity (weekly)
 - Adequate Relief of IBS Symptoms (weekly, after randomization)
 - Degree of Relief of IBS Symptoms (weekly, after randomization)

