10.7.5 Efficacy Variables

Efficacy variables in this trial will be captured via the IVRS on a daily basis (CSBM frequency, SBM frequency, consistency, straining, and abdominal symptoms of pain, discomfort, bloating, fullness, and cramping) or weekly basis (IBS severity, and constipation severity) during the screening (baseline) period and the 26 week treatment period. Adequate relief of IBS symptoms and degree of relief of IBS symptoms will be collected weekly during the treatment period. The IBS-QOL will be collected at the randomization visit, the week 12 visit, and the week 26 visit. Treatment satisfaction will be recorded at the end of each month during the treatment period through week 20 and again at week 26. Use of rescue medication is also collected daily throughout the screening and treatment period. Rescue medication usage is incorporated into the derivation of the efficacy variables but is not itself considered an efficacy variable.

The primary efficacy variable will be the overall responder rate. An overall responder will be defined as a weekly responder for the first 6/12 weeks where both CSBM and abdominal pain response criteria were met for the week. The CSBM and abdominal pain response criteria are defined below. The weekly overall responder rates will be summarized for each week of the treatment period.

The CSBM response criteria are defined as an increase of one or more change in average weekly CSBMs from baseline. The definition of a CSBM is as follows: A CSBM is a SBM for which the subject responds “yes” to the following question; “Did you feel like you completely emptied your bowels?” Any SBM which is preceded within 24 hours by the use of rescue medication will not be counted as a SBM and therefore also not counted as a CSBM as defined above. Should a subject not have data reported for a given week (either due to a gap in reporting or due to discontinuation), the subject will be considered to be a non-responder for the week.

A key secondary efficacy variable will be the overall CSBM responder rate. An overall CSBM responder will be defined as a weekly CSBM responder for the first 6/12 weeks where the CSBM response criteria were met for the week.

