A key secondary efficacy variable will be the overall CSBM responder rate. An overall CSBM responder will be defined as a weekly CSBM responder for the first 6/12 weeks where the CSBM response criteria were met for the week. The weekly CSBM responder rates will be summarized for each week of the treatment period. An endpoint week will be defined as the last valid week during the treatment period with a CSBM response criteria assessment.

The average weekly CSBMs will be calculated as the sum of the number of CSBMs reported during each day of the defined weekly period divided by the number of days CSBMs were reported multiplied by 7. A valid week will require at least 4 days of SBM reporting. The average weekly CSBMs and change from baseline (where baseline is the average of the 2-weeks during the screening period) for each week of the treatment period will be summarized. An endpoint week will be defined as the last valid week during the treatment period with an average weekly CSBM.

The abdominal pain response criterion is defined as a decrease of 30% or more of percent change in average weekly worst abdominal pain from baseline. Abdominal pain will be scored daily using the scale 0 = No pain to 10 = very severe pain. The average weekly abdominal pain score will be calculated as the average score for all days during a valid week. A valid week will require at least 4 days of abdominal pain reporting. Should a subject not have data reported for a given week (either due to a gap in reporting or due to discontinuation), the subject will be considered to be a non-responder for the week.

The average weekly abdominal pain score and percent change from baseline (where baseline is the average of the 2-weeks during the screening period) for each week of the treatment period will be summarized. An endpoint week will be defined as the last valid week during the treatment period with an average weekly abdominal pain score.

A key secondary efficacy variable will be the overall abdominal pain responder rate. An overall abdominal pain responder will be defined as a weekly abdominal pain responder for the first 6/12 weeks where the abdominal pain response criteria were met for the week.

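### The 24-hour rescue look-back can miss an evening dose when the next diary call is later, so a movement the analysis rule excludes can be counted as a CSBM

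*Protocol*

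**What the plan says.** - **Call window.** Daily diary calls may be made at any time from 6PM to 11:59PM local time (Protocol 4 and 8.1.2; SAP 2.2).
- **Rescue question.** Protocol 8.3.2.7 has two branches. If the previous day's diary was completed, the script asks "Have you taken any rescue medication over the past 24 hours". If it was not, it asks "Have you taken any rescue medication over the past 48 hours". A yes leads to questions on the date and time of the dose.
- **Bowel movement question.** Protocol 8.3.2.6 asks "How many bowel movements have you had in the past 24 hours", then the time of each movement (not its date) and whether emptying was complete.
- **Exclusion rule for analysis.** Protocol 10.7.5, repeated in SAP 2.3.1: "Any SBM which is preceded within 24 hours by the use of rescue medication will not be counted as a SBM", and so it is not a CSBM either.
- **Exclusion rule in the rescue section.** Under Protocol 5.5 a movement is not spontaneous "if it is reported less than 24 hours from the use of a rescue medication". The same section requires every rescue use and its time to be recorded in the daily call.
- **Weekly value.** SAP 2.3.1 takes the "sum of the number of CSBMs reported during each day of the defined weekly period", divides by the number of days reported and multiplies by 7. A valid week needs at least 4 days, and the CSBM criterion is an increase of at least 1 from baseline.
- **Screening.** Protocol 5.4 limits rescue to 2 of the 14 days, with none in the 48 hours before randomization. The IVRS checks diary eligibility electronically.

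**The concern.** To classify a movement reported in the past 24 hours under Protocol 10.7.5, the database must know about rescue in the past 48 hours. In the completed-diary branch the script asks about 24 hours and leaves the rest to the previous call. That works only if the two calls are no more than 24 hours apart, and the call window allows nearly 30. Neither question is tied to the time of the last call.

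At stake is the CSBM half of the primary endpoint. A movement that the analysis rule means to discard can enter the weekly count as spontaneous. Baseline CSBMs and the screening rescue count are exposed to the same gap. In addition, the protocol words the 24-hour exclusion in two ways that do not classify every movement alike.

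**Working it through.** **1. The plan's own figures.** The plan gives no figure for diary coverage. Its power statement (Protocol 10.1: 300 per arm, two-sided Fisher's exact test at 0.05) reproduces by exact enumeration: 96.1% for 45% v 30% (stated 95%), and 80.8% for 45% v 33.4% (stated 80%). Neither depends on the diary.

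**2. Spacing of calls.** The shortest spacing is 23:59 then 18:00, or 18 h 01 min. The longest is 18:00 then 23:59, or 29 h 59 min. Uncovered time = max(0, spacing − 24 h), at most 5 h 59 min, and only when the second call is later by the clock than the first. A dose taken between midnight and 6PM is at most 23 h 59 min old at that day's call, so only doses taken in the call window can be missed.

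**3. A case that fails.**
- Monday 7PM: call.
- Monday 10PM: bisacodyl.
- Tuesday 7AM: complete movement, 9 h after the dose.
- Tuesday 11PM: call. The look-back starts Monday 11PM. The movement (16 h earlier) is reported. The dose (25 h earlier, and after Monday's call) is not asked about by either call.

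Protocol 10.7.5 and SAP 2.3.1 would exclude this movement, but the diary data count it as a CSBM.

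**4. The look-back needed.** For a call at time c, reported movements lie in [c − 24 h, c], and rescue that can disqualify them lies in [c − 48 h, c]. The existing 48-hour question covers this exactly, but it runs only after a missed diary. Calls either side of one missed day can be 48 h + 5 h 59 min = 53 h 59 min apart. A dose can therefore still escape the record there, though not one that bears on a movement in the last 24 hours.

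**5. Chance that an evening dose is missed** (assumptions throughout; the documents give no call or dose times).
- Independent call times, uniform over the 6 hours: a dose at fraction u of the window is missed with probability u(1 − u). The maximum is 0.25 at 9PM and the mean is 1/2 − 1/3 = 1/6, or 17%.
- Calls uniform within a band of w hours, doses spread evenly over 6PM to midnight: mean gap = w/6 h, so the chance is (w/6)/6 = w/36. This gives 1.4% for w = 0.5, 2.8% for w = 1 and 5.6% for w = 2.

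**6. Effect of one misclassified CSBM on the weekly value.** It adds 7/k for k diary days: 1.0 (k = 7), 1.17 (6), 1.4 (5), 1.75 (4). Each meets an increase of 1 on its own.

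**7. The two exclusion rules side by side**, with daily calls at 7PM.
- Rescue Monday 3PM, movement Tuesday 7AM, reported Tuesday 7PM. Dose to report is 28 h, so Protocol 5.5 counts it. Dose to movement is 16 h, so Protocol 10.7.5 excludes it.
- Movement Tuesday 10AM, rescue Tuesday 3PM, reported Tuesday 7PM. Dose to report is 4 h, so Protocol 5.5 read literally excludes it. The movement came before the dose, so Protocol 10.7.5 keeps it.

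In step 3 the report comes 25 h after the dose, so Protocol 5.5 read literally would count the movement even if the dose were recorded. The misclassification is against Protocol 10.7.5 and SAP 2.3.1 only.

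**8. Illustration of the effect on the comparison** (not an estimate). With weeks treated as independent, turning 2% of non-response weeks into response weeks in both arms moves 30%/45% to 33.2%/48.2%; the difference stays at 15.0 points. If only placebo rose, to 32%, power would fall from 96.1% to 89.2%.

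**The case against.** The best case for the plan is that the question's look-back is not the only route for rescue data. The date and time fields would accept a dose 25 hours old. Protocol 5.5 requires all use to be recorded and tells subjects to contact the investigator before a dose. Protocol 5.6 puts concomitant therapy on the CRF, and visits include IVRS training. The exclusion rule also speaks of use, not of a yes to one question. This shows that some missed doses may be known. But the script does not prompt for them, and no section brings investigator contact or CRF records into the SBM/CSBM derivation.

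The effect may also be small. It needs a later call than the day before, a dose in the gap, and then a complete movement inside the next look-back. The week must also show the 30% pain reduction, and 6 of 12 such weeks are needed. The same error at baseline raises the bar and partly offsets it. All of this stands.

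On movements entered twice when the second call is earlier, recorded times allow duplicates to be found, and SAP 4 puts programming specifications in a separate document. The SAP's silence does not show that no check exists.

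A reader might infer three stronger things:
- *A sixth to a quarter of rescue doses are lost.* The 17% and 25% apply only to doses in the evening window and need independent, uniform call times.
- *The error favours placebo and pulls the result toward no effect.* The documents give no rescue frequency for either arm, so the direction is not established.
- *One misclassified movement makes a responder week.* It can supply only the CSBM half.

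**Conclusion.** The gap is real and follows from the plan's own clock times: up to 5 h 59 min between consecutive calls in which rescue is not asked about. A movement that Protocol 10.7.5 and SAP 2.3.1 would exclude can be counted as a result. The share of evening doses affected runs from about 1.4% for regular callers to 17% for wholly irregular ones, under assumed call and dose times. Net bias in the responder rates can be neither sized nor signed from the documents. Nothing in them shows that the primary comparison or its error rate is compromised. The case for acting is that the rule cannot be applied reliably to the data collected, and that the remedy costs little. The conflict between Protocol 5.5 and the analysis rule does not depend on any of these assumptions and affects even subjects who always call at the same hour.

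**What to change.** 1. **Rescue question.** Either of two changes works:
   - Ask the existing 48-hour question at every call. This is enough to classify every movement reported in the past 24 hours and removes one IVRS branch. It does not recover movements that fall in the gap.
   - Anchor both the rescue and the bowel movement questions to the last completed call. This also recovers those movements. A look-back longer than 24 hours would need the date of each movement as well as its time, and after a missed day the weekly divisor must match the days covered.
2. **SAP.** State that rescue doses and movements are de-duplicated by recorded time where two look-backs overlap.
3. **One exclusion rule.** Reconcile Protocol 5.5 with Protocol 10.7.5 and SAP 2.3.1 in a single wording, and use it in both the IVRS eligibility check and the analysis.

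For the first option the cost is one script change and a few lines of text, with no added question, visit or subject. The drawback is that some doses will be reported twice, possibly with slightly different times, so the de-duplication rule needs care.

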8.3.2.8 IBS Severity (weekly)

“How would you rate the severity of your IBS over the past week? Please use the following scale. Press 1 for None. Press 2 for Mild. Press 3 for Moderate. Press 4 for Severe. Press 5 for Very Severe.”

8.3.2.9 Constipation Severity (weekly)

“How would you rate the severity of your constipation over the past week? Please use the following scale. Press 1 for None. Press 2 for Mild. Press 3 for Moderate. Press 4 for Severe. Press 5 for Very Severe.”

8.3.2.10 Adequate Relief of IBS Symptoms (weekly)

“Have you had adequate relief of your IBS symptoms over the past week? Press 1 for Yes. Press 2 for No.”

8.3.2.11 Degree of Relief of IBS Symptoms (weekly)

“How would you rate the degree of relief of your IBS symptoms over the past week? Please use the following scale. Press 1 for Completely relieved. Press 2 for Considerably relieved. Press 3 for Somewhat relieved. Press 4 for Unchanged. Press 5 for Somewhat worse. Press 6 for Considerably worse. Press 7 for As bad as I can imagine.”

8.3.2.12 Treatment Satisfaction (completed at site, not IVRS)

At visits 4, 5, 6, 7, 8, and 9, subjects will be questioned about their overall satisfaction with the study drug’s ability to relieve IBS; with the following possible answers: 1= not at all satisfied, 2= a little satisfied, 3= moderately satisfied, 4 =quite satisfied, 5= very satisfied

8.3.2.13 Irritable Bowel Syndrome - Quality of Life (IBS-QOL) (completed at site, not IVRS)

On Day 1 (Visit 2), after randomization, and at Visits 6 and 9 (Day 85 and Day 183, at the end of the study), subjects will be questioned about their quality of life. The IBS-QOL (see [Appendix D](#)) measures 10 domains found to be relevant to patients with irritable bowel syndrome: emotional health, mental health, health belief, sleep, energy, physical functioning, diet, social role, physical role, and sexual relations. The IBS-QOL consists of 34 questions.

